5.1 Key Definitions

The following items below are standard terminologies discussed throughout the SAP.

5.1.1 Day 1/Date of First Dose

The date of first dosing of study drug is not collected on the CRF because subjects are given study drug to administer themselves. Since both compliance and missed doses were captured, it will be assumed that Day 1 is the same day as the first dosing day of study drug for subjects in the safety population later described in the SAP in [Section 6.1](#).

5.1.2 Study Day

Study day will be calculated in reference to Day 1 stated above in [Section 5.1.1](#). For assessments conducted on or after the Day 1 date, study day is calculated as the assessment date – Day 1 date + 1. For assessments conducted before the Day 1 date, study day is calculated as the assessment date – Day 1 date. There is no Study Day 0 in this study.

5.1.3 Not Reported

A not reported value may be displayed in a listing, summary statistics table, frequency table, shift table, etc. The not reported record could be due to a missed sample/measurement/assessment, missed visit, unable to calculate a value, or withdrawal from the study early.

5.1.4 Baseline and Post-Baseline Values

Unless otherwise specified, the baseline value is defined as the last measurement/assessment collected/derived on Day 1 or during screening. Unless otherwise specified, post-baseline values are defined as collected/derived measurements/assessments after Day 1.

For specific questionnaire assessments, missing responses on Day 1 will not be substituted for screening values for the baseline specific questionnaires. If the total score cannot be calculated at Day 1, then the screening visit will be used if the total score can be calculated at screening. If the total score cannot be calculated for both screening and Day 1 visits, then the latest individual values and subscale scores will be used for the baseline. All questions within a specific questionnaire will be paired together in an analysis visit for the baseline records.

5.1.5 Change from Baseline

If both post-baseline and baseline values are present/imputed, then change from baseline is defined as each post-baseline value – baseline value. Otherwise the change from baseline will not be reported.

5.1.6 Change from Treatment Periods

If both post-values and pre-values are present/imputed then change from treatment periods are defined as the following:

- Change from Week 2 (Placebo)
 - Post-values conducted at Weeks 3, 4, 5, 6, and Follow-up (Week 7)
 - Pre-value is defined as the last measurement/assessment collected/derived on Week 2 (end of the Placebo Period)
- Change from Week 4 (NYX-2925 20 mg PO QD)
 - Post-values conducted at Week 5, Week 6, and Follow-up (Week 7)
 - Pre-value is defined as the last measurement/assessment collected/derived on Week 4 (end of the NYX-2925 20 mg PO QD Period)
- Change from Week 6 (NYX-2925 200 mg PO QD)
 - Post-values conducted at Follow-up (Week 7)
 - Pre-value is defined as the last measurement/assessment collected/derived on Week 6 (end of the NYX-2925 200 mg PO QD Period)

Otherwise the change from treatment periods will not be reported.

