1. SYNOPSIS

Name of sponsor/company: Aptinyx Inc.	
Name of investigational product: NYX-2925	
Name of active ingredient: (2S, 3R)-3-hydroxy-2-((R)-5-isobutyryl-1-oxo-2,5-diazaspiro[3.4]octan-2-yl)butanamide	
Title of study: A Phase 2, Single-Blind, Exploratory, Placebo-controlled, Pilot Study to Assess the Efficacy and Safety of Daily Oral NYX-2925 in Subjects with Fibromyalgia	
Study Sites: Approximately 2 sites	
Investigators: Multicenter	
IND Number: 129731	
Studied period (years): Estimated date first subject enrolled (randomized): Approximately June 2017 Estimated date last subject completed: approximately November 2018	Phase of development: 2
Objectives 
Primary objective: Determine whether daily dosing with NYX-2925 20 or 200 mg changes the markers of central pain processing in subjects with fibromyalgia using functional magnetic resonance imaging (fMRI), resting state functional connectivity magnetic resonance imaging (rs-fcMRI) and proton magnetic resonance spectroscopy (¹H-MRS) on active drug versus placebo.Secondary objectives: To evaluate the safety of NYX-2925 in subjects with fibromyalgia.	
Exploratory analyses:	

Methodology:**Study Design**

The study will include up to a 30-day screening period, to confirm the diagnosis, assess eligibility, and complete the baseline magnetic resonance imaging (MRI). This is a single-blind, exploratory, placebo-controlled, pilot study in which eligible subjects will receive 2 weeks of daily oral placebo, 2 weeks of NYX-2925 20 mg PO daily (low dose), 2 weeks of NYX-2925 200 mg PO daily (high dose), followed by a 1 week follow-up period. An MRI will be conducted during the screening period, during the last week of the placebo period, during the last week of the NYX-2925 20 mg administration period, and during the last week of the NYX-2925 200 mg administration period. Study visits will occur during screening, then at Day 1 and weeks 1, 2, 3, 4, 5, 6, and 7. An optional MRI will be completed at the end of the follow-up period for consenting subjects. Study participants and study staff responsible for interpreting MRI results will be blinded to the study drug administration.

Study drug (NYX-2925 or matching placebo) will be dispensed to subjects for self-administration.

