6. INVESTIGATIONAL PLAN

6.1. Overall Study Design and Plan: Description

This is a single-blind, exploratory, placebo-controlled, pilot study to assess the efficacy and safety of daily oral NYX-2925 in fibromyalgia subjects. The study will include a screening period (up to 30 days), a placebo period, an active treatment period with 2 dose strengths, and a follow-up period as follows:

[figure not shown]
- Placebo PO QD for 2 weeks
- NYX-2925 20 mg PO QD for 2 weeks
- NYX-2925 200 mg PO QD for 2 weeks
- Follow-up for 1 week

Eligible subjects will receive MRIs during the screening period, during the placebo period, during the NYX-2925 20 mg PO QD period, and during the NYX-2925 200 mg PO QD period. Safety assessments will be conducted and adverse events will be collected during the study. Daily pain scores and other fibromyalgia scales will be collected for exploratory analysis. During the follow-up period, an optional MRI will be completed for consenting subjects in order to evaluate duration of effect.

[figure not shown]
Figure 1: Study Design

[figure not shown]
- MRI¹ - conducted during screening period
- MRI² - conducted between Weeks 1 and 2 of placebo administration
- MRI³ - conducted between Weeks 3 and 4 of NYX-2925 20 mg PO QD
- MRI⁴ - conducted between Weeks 5 and 6 of NYX-2925 200 mg PO QD
- MRI⁵ - (Optional) conducted at Week 7 ± 2 Days

Table 3: Schedule of Assessments

[figure not shown]
The table is completely obscured by a large black rectangular redaction box.

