5.5 Analysis Visits

Analysis visits are determined based on the collected/derived data for the study that will be used for listings and statistical analyses. In some events, there may be differences in visits depending on the data used for statistical summaries and as a result analysis visits are defined. For example, data for

efficacy versus safety may have different methods for defining the analysis visits. The subsections below represent the analysis visits that will be used to support the analyses in this SAP.

In the event more than one record is collected/derived within an analysis visit, the non-missing record with the date closest to the target day will be selected. If there is a tie between two dates between the target date, then the first date will be used. If more than one non-missing record occurs on the same date, then the first planned scheduled result will be used.

Clinical laboratory tests will also consider lowest, highest, and most abnormal post-baseline results as additional analyses. More details are provided in [Section 12.2](#).

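### The readable SAP study-day windows conflict with the protocol's MRI timing: a compliant placebo scan on Days 8-10 counts as Week 1 and leaves the subject with no reported change from placebo

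*SAP*

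**What the plan says.** **Scan timing.** The Protocol synopsis places the on-treatment scans "during the last week of the placebo period, during the last week of the NYX-2925 20 mg administration period", and likewise for 200 mg. The notes to Figure 1 in Protocol 6.1 say the same in visit terms: the placebo scan is "conducted between Weeks 1 and 2 of placebo administration", the 20 mg scan is "conducted between Weeks 3 and 4 of NYX-2925 20 mg PO QD", and the 200 mg scan lies between Weeks 5 and 6. One scan is planned per treatment period.

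**Analysis visits.** SAP 5.5 introduces its windows with "The subsections below represent the analysis visits that will be used to support the analyses in this SAP". The table in SAP 5.5.1 then assigns records by study day: Week 1 is Days 4-10, Week 2 is 11-17, Week 3 is 18-24, Week 4 is 25-31, Week 5 is 32-38 and Week 6 is 39-45.

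**Change from placebo.** SAP 5.1.6 fixes the reference: "Pre-value is defined as the last measurement/assessment collected/derived on Week 2 (end of the Placebo Period". Post-values may come from Weeks 3, 4, 5, 6 or follow-up. If either value is absent, "Otherwise the change from treatment periods will not be reported". SAP 5.4.4.2 requires both values for the paired tests. SAP 5.6.2 contains a double negative but is best read as no imputation.

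**The concern.** The primary objective is a comparison of active drug with placebo on imaging markers, and Protocol 12.5 specifies change from the end of the placebo period. With a single placebo scan per subject, that scan is the only possible reference. The SAP windows are centred on visit target days 7, 14, 21 and so on, whereas the protocol's scan windows run from one visit to the next. The boundary between two SAP visits therefore falls inside each scan window. A subject scanned exactly as the protocol allows could lose every change-from-placebo result through a derivation rule, with no second record to fill the gap.

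**Working it through.** **Inputs.** Scan windows: Protocol synopsis and 6.1. Visit windows: SAP 5.5.1. Pre- and post-value rules: SAP 5.1.6. Planned number, 24: Protocol synopsis. Two-sided paired t-test at 0.05: SAP 5.4.4. There is no planned figure to reproduce, because Protocol 12.1 and SAP 4.4 say the sample size does not rest on power.

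**Step 1: map scan days to SAP visits.** The last week of each two-week period is taken as its nominal days 8-14.

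| Scan | Nominal days allowed | Placed in the earlier visit | Placed in the end-of-period visit |
|---|---|---|---|
| Placebo | 8-14 | 8-10, Week 1 | 11-14, Week 2 |
| 20 mg | 22-28 | 22-24, Week 3 | 25-28, Week 4 |
| 200 mg | 36-42 | 36-38, Week 5 | 39-42, Week 6 |

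In each period 3 of 7 nominal days fall in the earlier visit. The protocol allows each visit ±2 days, so at the extremes the placebo scan window runs from Day 5 to Day 16. Then 6 of 12 days (5-10) are Week 1. The counts are the same for the two active periods.

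**Step 2: consequence under SAP 5.1.6.**
- Placebo scan early: no Week 2 pre-value, so no change from placebo is reported at 20 mg or at 200 mg.
- 20 mg scan early: the change from placebo is reported under Week 3 instead of Week 4. The Week 4 pre-value for later contrasts is missing.
- 200 mg scan early: the change from placebo is reported under Week 5 instead of Week 6. The Week 6 pre-value for the change to follow-up is missing.

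**Step 3: subjects who keep any change from placebo.** Let q be the share of placebo scans done early. This is an assumption, and dropout is ignored. Retained = 24 × (1 − q).
- q = 10%: 24 × 0.90 = 21.6, about 22
- q = 20%: 24 × 0.80 = 19.2, about 19
- q = 3/7 (uniform over the seven days): 24 × 4/7 = 13.7, about 14

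**Step 4: detectable effect.** For n pairs, solve for the standardized mean change d at which the paired t-test (n − 1 degrees of freedom, noncentrality d√n) has 80% power.
- n = 24: d = 0.60
- n = 22: d = 0.63
- n = 19: d = 0.68
- n = 14: d = 0.81

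**Step 5: the row split.** Suppose the same share q of 20 mg scans is early, independently of the placebo scan. The Week 4 row then holds 24 × (1 − q)² pairs and the Week 3 row 24 × (1 − q) × q.
- q = 10%: 19.4 + 2.2 = 21.6
- q = 20%: 15.4 + 3.8 = 19.2
- q = 3/7: 7.8 + 5.9 = 13.7

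The two rows add up to the subjects retained in Step 3. The split weakens each row but discards nobody further from the comparison with placebo.

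**The case against.** The strongest objection is that nobody outside the sponsor can see whether the 5.5.1 table governs imaging. SAP 5.4.4.2 ties the paired tests to the analysis visits given in Sections 9 and 10, and the imaging section, 9, is redacted. SAP 5.5 itself allows different kinds of data to use different visit definitions. The table's title names safety and efficacy, while the SAP files MRI under pharmacodynamics. This stands, and it limits certainty. No readable text exempts MRI, however. The second window table, which uses visit dates, does not fit MRI: its baseline is Day -7 to -1 and it leaves earlier screening values out of the summaries, whereas Protocol 10.1 lets the screening scan occur at any time in screening.

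Early scans may also be rare. Protocol 8.8 speaks of study visits that include imaging. If scans accompany the Week 2, 4 and 6 visits (±2 days), they fall on Days 12-16, 26-30 and 40-44, all inside the intended SAP windows. This is a fair point about frequency, and uniform timing has no support in the documents. The Figure 1 notes still permit earlier scans.

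Three stronger readings are tempting, and the documents do not support them:
- A reader might infer that an early active-dose scan also removes the subject from the comparison with placebo, leaving only 19, 15 or 8 pairs. SAP 5.1.6 accepts Weeks 3 and 5 as post-values, so those counts describe only the Week 4 minus Week 2 row, which no readable text names as primary.
- A reader might worry that the Week 2 window runs past the switch to 20 mg. With a Week 2 visit on Day 12, Days 13-17 still carry the Week 2 label. No scan is scheduled in those days, so this matters little for imaging.
- SAP 5.1.6 selects the last record in a visit, whereas SAP 5.5 says "the non-missing record with the date closest to the target day will be selected". The rules differ, but with one scheduled scan per period they would seldom pick different records.

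**Conclusion.** The conflict between the readable documents is real, and the day mapping is exact. Under the visible rules, a compliant placebo scan on nominal Days 8-10 leaves the subject with no reported change from placebo. An early active-dose scan moves to another row and costs some later contrasts. The subject stays in the efficacy population; what is lost is the pair.

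The size depends on an unknown share of early placebo scans. It is nil if every scan accompanies the end-of-period visit, about 2 of 24 subjects at 10%, about 5 at 20%, and about 10 under uniform timing. The detectable-effect figures illustrate lost information in an exploratory study that claims no power; they do not show that a target was missed. The whole point is also conditional on Section 9 not already assigning scans by period. Those limits make this a should-fix: the rule as readable works against the study's main comparison, but the loss is not established.

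**What to change.** In SAP 5.5 and 5.1.6, assign MRI records by treatment period from actual visit dates, as SAP 5.2 already does for treatment allocation. The single placebo, 20 mg and 200 mg scan then serves as the Week 2, Week 4 and Week 6 value respectively, and a scan on the visit day that closes a period belongs to that period. All 7 of 7 nominal days in each window then map to the intended visit, and no pair is lost to windowing. State one record-selection rule and use it in both sections. If Section 9 already assigns scans this way, add a sentence saying that it overrides the 5.5.1 table for imaging.

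The cost is SAP wording and one derivation, with no new data. It is best settled before the interim cut after the 11th completer (SAP 14), where each lost pair weighs most.

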5.1.7 Percent Change from Baseline

If the baseline value is not equal to zero or missing and the change from baseline value is present/imputed, then the percent change from baseline is defined as $100 \times (\text{change from baseline} / \text{baseline})$ and is rounded off to 1 number after the decimal point. Otherwise the percent change from baseline will not be reported.

5.2 Treatment Allocation

Subjects are planned to receive multiple study drug treatments in the study. Therefore, the following treatments will be assigned during these periods:

- Screening Visit until 1 Day Prior to the Day 1 (Baseline) Visit: No Treatment
- Day 1 (Baseline) Visit until the Week 2 Visit: [REDACTED]
- 1 Day After Week 2 Visit until the Week 4 Visit:
 - If any adverse events and/or concomitant medications start on the Week 2 visit, then those records will be assigned to the [REDACTED] treatment arm.
- 1 Day After Week 4 Visit until the Week 6 Visit:
 - If any adverse events and/or concomitant medications start on the Week 4 visit, then those records will be assigned to the [REDACTED] treatment arm.
- 1 Day After Week 6 Visit until the Follow-Up (Week 7) Visit: [REDACTED]
- Unscheduled or Early Termination Visits: Last Study Drug Dispensed and Taken

5.3 Treatment Group Comparisons

The following treatment groups will be summarized in the statistical tables:

- Placebo
- NYX-2925 20 mg PO QD
- NYX-2925 200 mg PO QD
- All Doses of NYX-2925
 - Pooled for adverse events, concomitant medications, and study drug treatment compliance and exposure tables.
- Not Treated
 - This will only be displayed for the analysis population table that presents subjects screened, but were not enrolled in the study or dispensed study drug.
- All Subjects
 - This will only be displayed for the analysis population and concomitant medications tables.

The following changes in treatment period comparisons will be performed for efficacy:

- Change from Baseline
- Change from Week 2 [REDACTED]
- Change from Week 4 [REDACTED]
- Change from Week 6 [REDACTED]

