4.6 Analyses Changes from the Protocol

In Section 12.6.1 of the protocol, it states that TEAE summaries will be provided separately for each study period and the follow-up period. TEAEs will be summarized and grouped based on the last study drug treatment the subject received compared to the start date of the event explained in [Section 5.2](#). The rest of the analyses stated in the protocol support the analyses planned in this SAP.

5. General Statistical Principles

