5.4.2 Frequency Distributions

Frequency distributions (count [n], percentage of subjects [%], and not reported) will be used to summarize categorical or qualitative variables. In general, the denominator for the percentage calculation will be based upon the total number of subjects in the study population for the treatment groups for that particular time point assessment. Records that are missing or not done will be displayed as “Not Reported” and will not be factored into the percentage calculation, unless otherwise specified. Percentages will be presented to a maximum of one number after the decimal place.

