8.1 Study Drug Accountability

Subjects will be dispensed study drug based on fixed treatment periods at visits Day 1 (Baseline), Week 2, and Week 4. In the event the subject comes in for an unscheduled visit prior to a weekly visit, they may be dispensed additional study drug. Additional study drug may be dispensed at any study visit or unscheduled visit if the subject will need study drug beyond the two week allotment

provided at Day 1, Week 2 and Week 4. Capsule strengths for NYX-2925 are 10 mg and 100 mg. Subjects will be instructed to take 2 capsules of investigational product once daily by mouth.

The following data will be collected and derived at each start and end to the study drug accountability treatment periods/visit intervals:

Parameter	Origin/Derivation
Capsules Dispensed Amount	CRF
Capsules Returned Amount	CRF
Expected Number of Capsules Taken	Derived: Date Returned – Date Dispensed + 1 (where the maximum would be 30 because 30 capsules are issued at each dispensing visit)
Estimated Number of Capsules Taken	Derived: Number of Capsules Dispensed Amount – Number of Capsules Returned Amount
Treatment Compliance (%)	Derived: $100 \times \frac{\text{Estimated Number of Capsules Taken}}{\text{Expected Number of Capsules Taken}}$ (rounded off by one number after the decimal point)

The Overall NYX-2925 Treatment Compliance (%) will be calculated as:

- $100 \times \frac{\sum (\text{Estimated Number of Capsules Taken at All Study Drug Return Visits After NYX-2925 20 mg or 200 mg PO QD was Dispensed})}{\sum (\text{Expected Number of Capsules Taken at All Study Drug Return Visits After NYX-2925 20 mg or 200 mg PO QD was Dispensed})}$ and rounded off by one number after the decimal point

A subject will be classified as being compliant with study drug administration if their calculated compliance by each treatment period and overall is between 80% and 125%, inclusive. Descriptive statistics will be summarized for treatment compliance by returning analysis visits Week 2 (Placebo), Week 4 (NYX-2925 20 mg PO QD), Week 6 (NYX-2925 200 mg PO QD), and Overall (NYX-2925 20 mg and 200 mg PO QD). The following categorical ranges will be summarized in a table for those same analysis visits and overall:

- <80%, 80-125%, >125%, and Not Reported

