8.2 Study Drug Exposure

The study will include the following fixed placebo period and active treatment periods with 2 dose strengths:

- Placebo PO QD for 2 weeks
- NYX-2925 20 mg PO QD for 2 weeks
- NYX-2925 200 mg PO QD for 2 weeks

Each bottle number assigned to a subject will be verified that correct study drug was given based on the each treatment period. Any incorrect study drug bottle given where the estimated number of capsules taken defined in [Section 8.1](#) is greater than zero, will be defined as a major protocol deviation. Study drug exposure will be listed and summarized based on the treatment periods the subjects received.

The number of study days of study drug exposure will be summarized using descriptive statistics based on the date of the last dose of study drug collected on the CRF for each treatment period. If the date/time of the last dose of study drug was not fully collected for a treatment period, then the date of returning the study drug will be used instead. If a subject is lost to follow-up after being dispensed study drug and the date of the last dose of study drug was not collected, then the number of study days will be set to missing for that specific treatment period.

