12.1 Adverse Events

Treatment-emergent adverse events (TEAEs) will be those occurring during or after administration of the first dose of study drug until 30 days after the final dose of study drug. The date and time of first dose of study drug was not collected on the CRF for all subjects. Therefore, the following algorithm will be used to determine if the adverse events are treatment-emergent without a date and time of first dose of study drug:

- Earliest Possible AE Start Date \geq Day 1 (Baseline) Visit and Study Drug Dispensation **and**
- Latest Possible AE Start Date \leq 30 Days After the Final Dose of Study Drug

AEs that started prior to first dosing of study drug, but become worse in severity after receiving study drug will be considered treatment-emergent. The determination of whether or not an adverse event is classified as “treatment emergent” (i.e. TEAE) is not determined by the classification of “relationship

to study drug" collected on the CRF, but rather by the temporal relationship of the adverse event to the administration of study drug.

A related study drug TEAE is defined as any TEAE with at least a possible relationship to the study drug as assessed by the investigator or that is missing the assessment of causal relationship whose relationship to the study drug could not be ruled out. Relationships of "possibly related", "probably related", or missing are collected on the CRF, then those adverse events will be considered related study drug TEAEs. If the "unrelated" or "unlikely related" are collected on the CRF, then those adverse events will be considered not related study drug TEAEs.

Severity is assigned to each adverse event collected on the CRF. Maximum severity has the following order: "life threatening", "severe", "moderate", and "mild" as possible collection options on the CRF. A missing severity will be treated as "unknown" for analysis purposes.

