All adverse events will be coded and summarized by System Organ Class (SOC) and Preferred Term (PT) based on Medical Dictionary for Regulatory Activities (MedDRA) version 19.0 coding dictionary. This data will be summarized in a frequency distribution. Subjects may have more than one TEAE record per SOC and PT. At each level of subject summarization, a subject will be counted once if he/she reports one or more TEAE record at that specific level. For tables summarized by SOC and PT, the events will be displayed in the order of descending frequency counts for all treatments by SOC and then PT within SOC.

The number of subjects with at least one of the following adverse events, percentages for each category by treatment, and the number of total events will be included in an overall treatment-emergent adverse events summary table:

- Any TEAEs
- Related TEAEs
- Maximum Severity TEAEs
- Serious TEAEs
- Related, Serious TEAEs
- TEAEs Leading to Study Discontinuation
- Related TEAEs Leading to Study Discontinuation
- TEAEs Leading to Death

[figure not shown]
Summaries including the number of subjects and percentages of the following adverse events by SOC and PT will be provided:

- Any TEAEs
- Related TEAEs
- Maximum Severity TEAEs
- Serious TEAEs
- TEAEs Leading to Study Discontinuation

Additionally, TEAEs will be summarized by descending frequency counts of PT for all treatments. All adverse event data collected will be provided in subject listings. Subset subject listings will also be provided by serious treatment-emergent adverse events and deaths; by treatment-emergent adverse events leading to study discontinuation; any adverse events that are not considered to be treatment-emergent; by serious adverse events and deaths that are not considered to be treatment-emergent; and by adverse events leading to study discontinuation that are not considered to be treatment-emergent.

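### The pooled All Doses adverse-event column covers about twice the dosing days of the placebo column, and the readable SAP text reports only subject percentages and raw event totals

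*SAP*

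**What the plan says.** Every subject takes placebo, then 20 mg, then 200 mg, for 2 weeks each and in that order (SAP 4.1; protocol 6.1). There is no randomization.

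SAP 5.3 lists table columns for placebo, 20 mg, 200 mg and All Doses of NYX-2925. The last is "Pooled for adverse events, concomitant medications, and study drug treatment compliance and exposure tables".

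For adverse events, SAP 12.1 counts a subject once at each level of the summary. In the overall table, "percentages for each category by treatment, and the number of total events will be included". The tables by system organ class and preferred term give numbers and percentages of subjects. SAP 5.4.2 sets the general rule for percentages: "the denominator for the percentage calculation will be based upon the total number of subjects in the study population for the treatment groups". That denominator is subjects, not time.

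Exposure is handled separately in SAP 8.2: "The number of study days of study drug exposure will be summarized using descriptive statistics". By SAP 5.3 those tables carry the pooled column too. SAP 5.4.3 rules out formal testing of safety data. The list of planned tables in SAP section 15 cannot be read, and the mock shells are a separate document.

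**The concern.** A subject enters the All Doses count if an event starts in either of two periods, but enters the placebo count only through one. Pooling can therefore only keep or raise the number of subjects counted relative to either dose column. A higher All Doses percentage could come from the longer window alone.

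Safety is the secondary objective (protocol 5.2), and these descriptive tables are the main display of adverse events. Placebo is the only non-drug column beside the doses, so readers will naturally set All Doses against it. What is at stake is how one column is read, not the error rate of a test.

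**Working it through.** The documents state no adverse-event rate, so there is no figure of the plan's own to reproduce. The check asks what the columns would show if the drug did nothing.

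**Inputs from the documents.** Period length is 14 days each (SAP 4.1). All Doses covers 14 + 14 = 28 dosing days (SAP 5.3). Planned enrolment is about 24 (SAP 4.3).

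**Assumptions.** The placebo-period percentage p is 10, 20 or 40%. The event rate is constant and the same in every subject. There is no drug effect and no dropout, and the columns are treated as independent.

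**Subjects with at least one event.** At a constant rate, P(event within D days) = 1 − (1 − p)^(D/14). For 28 days this is 1 − (1 − p)².

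| Placebo, 14 d | All Doses, 28 d | Expected subjects of 24 | Chance All Doses shows more subjects than placebo |
|---|---|---|---|
| 10% | 1 − 0.90² = 19% | 2.4 v 4.6 | 76% |
| 20% | 1 − 0.80² = 36% | 4.8 v 8.6 | 86% |
| 40% | 1 − 0.60² = 64% | 9.6 v 15.4 | 94% |

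The last column comes from exact binomial calculations with n = 24. As a benchmark, two equal 14-day columns at 20% give either one the higher count in 43% of trials, with 14% ties.

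**Whole row.** At p = 20%, leaving follow-up time aside, the expected row is placebo 20%, 20 mg 20%, 200 mg 20%, All Doses 36%.

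**Event totals.** These scale with time: 28/14 = 2.0. At p = 20% the event rate is −ln(0.80) = 0.223 per subject per 14 days. Expected events are 24 × 0.223 = 5.4 on placebo and 24 × 0.446 = 10.7 under All Doses. Divided by 24 × 2 = 48 and 24 × 4 = 96 subject-weeks, both give 0.112 per subject-week, so the artefact disappears.

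**Relaxing the assumptions at p = 20%.**
- Subjects differ in proneness to events (gamma frailty of variance v, shared across a subject's periods). H = ((1 − p)^(−v) − 1)/v, and P(28 d) = 1 − (1 + 2vH)^(−1/v). For v = 1, H = 0.25 and P = 33%; for v = 2, H = 0.281 and P = 31%. By simulation, All Doses exceeds placebo in 84% and 82% of trials.
- A fraction d stops after 20 mg. The All Doses percentage is (1 − d) × 36% + d × 20%. For d = 10% this is 34%, for d = 20% it is 33%; All Doses is higher in 84% and 80% of trials.
- The rate falls over time. The excess vanishes if the later rate is 14/28 = 0.50 of the placebo-period rate. Counting by onset also works in this direction, because an event that persists from the placebo period without worsening is not counted again.

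**The case against.** The strongest reply is that the planned table exposes the artefact itself. If the drug is inert, a reader sees 20, 20, 20 and 36% side by side, and the two dose columns equal to placebo show that the excess comes from pooling. This largely stands, and is the main reason the severity is low. It does not make the pooled column comparable with placebo, and with about 5 subjects expected in a column the observed row will rarely be so tidy.

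Second, no comparison of All Doses with placebo is planned. The comparisons named in SAP 5.3 are for efficacy, and safety is untested. This stands. A reader might infer that the plan is likely to produce a false safety finding, but the documents do not support that: the percentages of trials above describe how a display behaves, not an error of any planned analysis.

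Third, the overall table gives event totals and SAP 8.2 gives exposure days in the same columns, so a reader could divide one by the other. This stands in part. The division spans two tables, and the tables by organ class and term list no event totals. Exposure also stops at the last dose, while SAP 12.1 counts onsets "until 30 days after the final dose of study drug", so the two intervals need not match.

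Fourth, a reader might infer that the imbalance is larger still, with the follow-up week falling to 200 mg and to All Doses. SAP 4.6 invites this: "TEAEs will be summarized and grouped based on the last study drug treatment the subject received compared to the start date of the event". But the label for "1 Day After Week 6 Visit until the Follow-Up (Week 7) Visit" in SAP 5.2 is blacked out, so the allocation cannot be read and must not be treated as missing. No figure here relies on it.

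Finally, fixed order confounds drug with time whatever is done about days at risk. That is true, and no rate removes it; unequal time is the part that can be removed.

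**Conclusion.** The point holds in limited form. On the readable text, the All Doses adverse-event column covers 28 nominal dosing days against 14 for placebo and is shown as subject percentages and raw totals. With an inert drug and a constant rate, 10, 20 or 40% on placebo becomes 19, 36 or 64% under All Doses, and expected events double. The direction survives the frailty and dropout checks, but not a halving of the event rate after the placebo period. The placebo percentages are assumed.

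The problem is confined to one descriptive column; the single-dose columns are nominally matched to placebo in time, apart from any follow-up time. It would go too far to say that the plan contains no adjustment at all, because the table list is unreadable and the shells are separate; a rate table or footnote there would already meet the point. Severity: low.

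**What to change.** In the overall treatment-emergent table, add a line of events per subject-week for placebo, 20 mg, 200 mg and All Doses. Count person-time over the same interval in which SAP 5.2 attributes onsets to each column, so that numerator and denominator agree whatever that allocation is. Add a footnote giving the nominal days at risk per column and stating that fixed treatment order still confounds any comparison with placebo.

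The cost is one line and one footnote, with no new data. The downsides are small. Person-time is partly approximate, because the date of first dose is assumed to be Day 1 (SAP 5.1.1) and an incompletely recorded last-dose date is replaced by the return date (SAP 8.2). Rates in about 24 subjects will be imprecise and should be read as description only.
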